Protocol

Study Title: Using Social Connectedness to Increase Physical Activity

Identifier: NCT04573972

Unique Protocol ID: STUDY2019_00000296

Date: October 22, 2021

Hypotheses

Hypotheses are pre-registered at ClinicalTrials.gov NCT04573972

<https://clinicaltrials.gov/ct2/show/NCT04573972>

We hypothesize that, compared to the regular incentive condition, participants in the social incentive condition will show a larger positive change in daily steps walked during the baseline period to daily steps walked in the post-intervention period.

Study Design

Participants volunteered for the study with a friend; thus randomization occurs at the level of the dyad, with half the dyads assigned to the regular incentive condition and half to the social incentive condition. During a 5-week protocol, participants complete a 1-week baseline period, a 2-week incentive period and a 2-week post-incentive period.

Communication with participants occurred using the Way to Health (W2H) platform. Participants downloaded the FitBit and Aware apps onto their IOS or Android smart phone to track steps walked and GPS location. They completed surveys on W2H at the beginning and end of the survey. W2H sent participants text messages each morning and evening. During the baseline period participants earned \$1 for each day they synced both apps. After the baseline period all participants were assigned a daily step goal that represented a 30% increase in daily steps walked. During the incentive and post-incentive periods, the evening text message included a link to a survey where participants could self-report walking with their partner. During both of these periods, participants earned \$1 per day for syncing the apps and an additional \$1 per day for completing the evening survey. During the incentive period only, they earn \$2 per day for meeting their step goal (regular incentive) or they earn \$1 per day for meeting their step goal and an additional \$1 per day for walking at least 1 mile with their partner. At the completion of the study, participants were mailed a ClinCard debit card loaded with their payment total.

Randomization

Simple randomization to condition was accomplished via the W2H platform at the completion of the baseline period. Because W2H does not have the capacity to randomize at the level of the dyad, the research team manually adjusted conditions such that both members of a dyad were in the same study condition.

Data collection procedures

Study participants were recruited at Carnegie Mellon University through posting on the subject pool website and announcements to undergraduate classes. Potential participants had to sign up with a friend, with at least one member of the friend pair being a current CMU student. Participants had to own an IOS or Android smartphone and be willing to download the FITBit and Aware apps to track their activity and location for 5 weeks.

Stopping rule

Our stopping rule was to close enrollment once 220 people were fully enrolled or when Oct 15, 2020 occurs, whichever comes first. We opened enrollment on Oct 1, 2020 and closed it on Oct 11, 2020 because at that point 220 people had fully enrolled. Fully enrolling includes consenting, completing the intake survey, providing a code for a partner who was also enrolling, and downloading the FitBit and Aware apps. Some of the individuals who fully enrolled were not included in the study because their partner did not fully enroll.

Manipulated variables

There was one manipulated variable (treatment condition) with two levels: regular vs. social incentive.

Measured variables

Primary dependent variables (as pre-registered on Clinical Trials)

1. The mean daily treatment period step count (averaged across all of a participant's included treatment period days) minus the mean daily baseline period step count (averaged across all of a participant's included baseline period days).
2. The mean daily followup period step count (averaged across all of a participant's included followup period days) minus the mean daily baseline period step count (averaged across all of a participant's included baseline period days).
3. Number of days during treatment period when participant reached goal. Converted to a fraction by dividing by the number of included treatment period days.

4. Number of days during followup period when participant reached goal. Converted to a fraction by dividing by the number of included followup period days.
5. Change in score on UCLA Loneliness Scale. Score on post-test (range 0 to 60) minus score on pretest.

Secondary dependent variables (as pre-registered on Clinical Trials)

6. Number of days participant walked together with partner during treatment period, as assessed via self-report on daily survey
7. Number of days participant walked together with partner during followup period, as assessed via self-report on daily survey
8. Number of days participant walked together with partner during treatment period, as assessed via Aware data
9. Number of days participant walked together with partner during followup period, as assessed via Aware data

Indices

The UCLA Loneliness Scale is measured on both the intake and exit surveys. It consists of 20 items, each scored as 0, 1, 2, or 3. The scores from all 20 items are added to form a total score ranging from 0 to 60.

Inclusion Criteria

In order to be included in the study, each participant must fulfill all of the following

- Consent
- Fully enroll, including authorizing FitBit app and installing Aware app
- Link to a friend who fully enrolls in the study before the registration deadline
- Participants who request to unenroll are excluded.
- Provide synced step data for at least one day of the 7-day baseline period
 - That is, there must be at least one baseline day with a non-zero step count
- Provide Aware data for at least one day of the 7-day baseline period

Exclusion of individual data points

- Days that a participant has a value of 0 for steps walked will be considered missing data (assume there was no sync for that day)
- For each participant, we will compute the mean and standard deviation of number of daily steps, computed over all days of the study with non-zero step counts. Days with a step count that are > 3 standard deviations away from the participant's own mean will be excluded from analyses (treated as missing data).

- Average step count will then be computed for each phase, after treating these excluded data points as missing.

Missing data

When a participant is missing step data for an individual day, the mean daily step count for the study phase will be computed using the days with non-missing data. If a participant is missing step data for all the days in a study phase, the mean daily step count for the baseline period will be substituted (leading to a change score of 0).

If a participant is missing data from the intake survey (e.g., gender, age, or UCLA loneliness score), the study-wide mean or mode will be substituted. If a participant is missing data from the exit survey (e.g, UCLA loneliness score), the corresponding value from the intake survey will be substituted.

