Analysis Plan

Study Title: Using Social Connectedness to Increase Physical Activity

Identifier: NCT04573972

Unique Protocol ID: STUDY2019_00000296

Date: October 22, 2021

Hypotheses

Hypotheses are pre-registered at ClinicalTrials.gov NCT04573972

<https://clinicaltrials.gov/ct2/show/NCT04573972>

We hypothesize that, compared to the regular incentive condition, participants in the social incentive condition will show a larger positive change in daily steps walked during the baseline period to daily steps walked in the post-intervention period.

Study Design

Participants volunteered for the study with a friend; thus randomization occurs at the level of the dyad, with half the dyads assigned to the regular incentive condition and half to the social incentive condition. During a 5-week protocol, participants complete a 1-week baseline period, a 2-week incentive period and a 2-week post-incentive period.

Communication with participants occurred using the Way to Health (W2H) platform. Participants downloaded the FitBit and Aware apps onto their IOS or Android smart phone to track steps walked and GPS location. They completed surveys on W2H at the beginning and end of the survey. W2H sent participants text messages each morning and evening. During the baseline period participants earned \$1 for each day they synced both apps. After the baseline period all participants were assigned a daily step goal that represented a 30% increase in daily steps walked. During the incentive and post-incentive periods, the evening text message included a link to a survey where participants could self-report walking with their partner. During both of these periods, participants earned \$1 per day for syncing the apps and an additional \$1 per day for completing the evening survey. During the incentive period only, they earn \$2 per day for meeting their step goal (regular incentive) or they earn \$1 per day for meeting their step goal and an additional \$1 per day for walking at least 1 mile with their partner. At the completion of the study, participants were mailed a ClinCard debit card loaded with their payment total.

Randomization

Simple randomization to condition was accomplished via the W2H platform at the completion of the baseline period. Because W2H does not have the capacity to randomize at the level of the dyad, the research team manually adjusted conditions such that both members of a dyad were in the same study condition.

Explanation of existing data

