The study protocol was pre-registered at ClinicalTrials.gov NCT04573972 <https://clinicaltrials.gov/ct2/show/NCT04573972> prior to any data collection. Clinical Trials pre-registrations do not include analysis plans. Consequently, this OSF pre-registration, including an analysis plan, was filed prior to downloading any data from W2H.

Participant flow diagram: ([name] or [name], please fill in numbers)

XXX people entered W2H portal	→ XX did not consent
↓ XX consented	→ XX did not fully enroll
↓ XX fully enrolled	→ XX not linked to a fully-enrolled partner
↓ XX has fully-enrolled partner	→ XX did not provide synced FitBit & Aware data for at least 1 out of 7 days of pre-intervention period or has partner who did not provide synced data for 1 out of 7 pre-intervention days
↓ XX provides baseline data	→ XX requested to be unenrolled prior to randomization
↓ XX included in study and randomized to condition (N= XX/2 pairs)	
↓ XX in the regular incentive condition & YY in the social incentive condition	

Data collection procedures

Study participants were recruited at Carnegie Mellon University through posting on the subject pool website and announcements to undergraduate classes. Potential participants had to sign up with a friend, with at least one member of the friend pair being a current CMU student. Participants had to own an IOS or Android smartphone and be willing to download the FITBit and Aware apps to track their activity and location for 5 weeks.

Stopping rule

Our stopping rule was to close enrollment once 220 people were fully enrolled or when Oct 15, 2020 occurs, whichever comes first. We opened enrollment on Oct 1, 2020 and closed it on Oct 11, 2020 because at that point 220 people had fully enrolled. Fully enrolling includes consenting, completing the intake survey, providing a code for a partner who was also enrolling, and downloading the FitBit and Aware apps. Some of the individuals who fully enrolled were not included in the study because their partner did not fully enroll.

Manipulated variables

There was one manipulated variable (treatment condition) with two levels: regular vs. social incentive.

Measured variables

Primary dependent variables (as pre-registered on Clinical Trials)

1. The mean daily treatment period step count (averaged across all of a participant's included treatment period days) minus the mean daily baseline period step count (averaged across all of a participant's included baseline period days).

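### Partners' conditions were matched by hand after the platform's draw, with no rule, masking or timing given: between 0% and about 50% of dyads may rest on staff choice, and the change-score models would not absorb a resulting baseline imbalance

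*Protocol*

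**What the plan says.** Study Design, in both documents, states that "randomization occurs at the level of the dyad", with half the dyads in each condition. The Randomization section then says that W2H carried out simple randomisation when baseline was complete. It gives the platform's limitation ("Because W2H does not have the capacity to randomize at the level of the dyad") and then describes how partners came to share an assignment: "the research team manually adjusted conditions such that both members of a dyad were in the same study condition". The SAP repeats the Protocol here and adds no rule.

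Five other places bear on the point:

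- Protocol, Data collection procedures: "Potential participants had to sign up with a friend". The pairs were therefore fixed at enrolment; only their conditions were adjusted later.
- Protocol, Study Design: "After the baseline period all participants were assigned a daily step goal that represented a 30% increase in daily steps walked". The order of goal-setting and manual matching is not given.
- SAP, Participant flow diagram: people are removed before randomisation if they, or their partner, lack baseline data ("XX did not provide synced FitBit & Aware data for at least 1 out of 7 days of pre-intervention period"). The box "XX included in study and randomized to condition (N= XX/2 pairs") follows. There is no box for changed assignments.
- SAP, Data File Structure: neither file lists condition, original draw or a changed assignment. The Study file does list the dates on which baseline and the incentive period started.
- SAP, Main Analysis: the covariates are time-zone match, gender, age, baseline start date (individual level) and enrolment lag between partners (dyad level). Baseline steps are not among them.

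**The concern.** Random allocation is the basis for comparing the two incentive conditions. When two partners drew different conditions, one draw had to be overridden. A rule fixed in advance and blind to the data, such as always keeping a designated partner's draw, leaves a valid randomisation by dyad. A case-by-case decision by someone who knew the participants or their data does not. The documents do not let a reader tell which of these happened.

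Timing matters because the draw came at the end of baseline, when a week of step data existed. The enrolment-lag and individual baseline-date covariates also allow for partners who reached that point on different days, so one partner might have learned a condition before the other's was settled. The documents do not say that this occurred.

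The analysis offers limited protection. Outcomes 1 and 2 are changes from baseline. If one arm starts higher by selection, regression to the mean makes its change look smaller, and a model without baseline steps does not correct this. Goal attainment (outcomes 3 and 4) could be reached by the same route, because the goal is a percentage increase on steps walked.

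**Working it through.** The documents give no figure for mismatched or changed dyads, so there is nothing to reproduce.

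**1. How many dyads needed a manual change**

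Inputs: 220 people fully enrolled (Stopping rule), so at most 220/2 = 110 dyads. The same section says that some were left out because a partner did not enrol, so the true number is below 110; 80 is used as an assumed lower case. Independent individual draws at p = 0.5 are inferred from simple randomisation on a platform that could not draw by dyad.

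P(draws differ) = 2p(1 − p) = 2 × 0.5 × 0.5 = 0.50. At p = 0.4 or 0.6 it is 0.48.

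| Dyads | Expected mismatches | Binomial 95% range |
|---|---|---|
| 110 (ceiling) | 55 | 45–65 |
| 80 (assumed) | 40 | 31–49 |

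These are dyads changed by hand. The share that rests on staff choice runs from 0% (a fixed blind rule) to about 50% (choice in every mismatch).

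**2. What selective choice could do (illustration only)**

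Assumptions, none taken from the documents: within mismatched dyads, choice produces a between-arm gap of *d* SDs of dyad-mean baseline steps; the baseline-to-later correlation is *r*; variances are equal; half the dyads are mismatched; there is one mean per dyad; the test is two-sided at 0.05 (the SAP sets alpha at .05 without saying whether tests are one- or two-sided).

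- Overall baseline gap = 0.5*d*.
- Spurious change difference = 0.5*d*(1 − *r*) baseline SDs.
- The SD of change is √(2(1 − *r*)) baseline SDs, so the bias is 0.5*d*√((1 − *r*)/2) SDs of dyad-mean change.
- SE = 2/√n in the same unit: 0.224 for 80 dyads, 0.191 for 110.

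| *d* | *r* | Bias (SD of dyad-mean change) | Type I error, 80 dyads | Type I error, 110 dyads |
|---|---|---|---|---|
| 0.25 | 0.9 | 0.028 | 5.2% | 5.2% |
| 0.5 | 0.7 | 0.097 | 7.2% | 8.0% |
| 1.0 | 0.5 | 0.250 | 20% | 26% |

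In participant-level SDs, multiply by √((1 + ICC)/2). For an assumed ICC of 0 to 0.5 the factor is 0.71 to 0.87, so 0.25 becomes about 0.18 to 0.22.

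**3. Whether the remedies would work**

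The last row was simulated at 110 dyads with no true effect (6,000 trials):

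| Model | Bias (SD) | Type I error |
|---|---|---|
| Change score without baseline steps | 0.250 | 25.6% |
| Baseline steps added | 0.001 | 5.4% |
| Only dyads whose draws agreed | 0.001 | 5.1% |

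**4. Cost of restricting to dyads whose draws agreed**

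SE ratio = √(n/(n − mismatches)) = √2 = 1.41 at 50%. Over the 95% ranges it is 1.30 to 1.56 for 110 dyads and 1.28 to 1.61 for 80.

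**The case against.** The strongest reply is that this is a reporting gap. A fixed rule fits the wording, would be valid, and would answer the question of validity once stated. The SAP also says that it "was filed prior to downloading any data from W2H", and the flow diagram's count in pairs suggests that both partners were assessed before either was assigned.

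Much of this stands:

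- A reader might infer that half the dyads were allocated by staff. The documents do not support that: about 50% is the share needing a change, it depends on inferred independent draws, and the share resting on choice may be zero.
- A reader might infer that staff were using baseline steps when they matched conditions. That is not established. Goal-setting is not placed before matching, and the flow-diagram screen asks only whether data exist, not how many steps were walked.
- A reader might infer that partners were drawn or notified on different days. The covariates allow for it but do not show it.
- The bias and type I figures have no anchor in the documents, and the 110-dyad column is a ceiling. The Main Analysis exclusions can only lower the number analysed.

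Two things do not fall away. Filing the plan before download says nothing about what staff could see inside the platform. And overriding draws by hand is a stated procedure, not merely an omitted detail: it can break randomisation, and the files as listed could not later show whether it did.

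**Conclusion.** The point holds as a cheap improvement. Both documents describe allocation by dyad that was in fact reached through platform draws matched by hand, at or after the end of baseline, with no rule, masking or timing for the matching.

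Under inferred independent 1:1 draws, about half the dyads needed a change. Between none and about half rest on staff choice, and the documents do not say where in that range the trial falls. If a fixed blind rule was used, the consequence for validity is nil. If choice tracked baseline steps, the assumed scenarios give 0.03 to 0.25 SDs of dyad-mean change, with type I error of about 5% to 20% at 80 dyads and 5% to 26% at 110. These figures show what the planned model would let through; they do not estimate what happened. The documents do not support a conclusion that allocation was biased or that the trial was not randomised.

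**What to change.** 1. **Record and report.** Add each participant's original W2H draw and final condition to the Study file; with the dyad id, changed assignments can then be derived. Report the number and direction of changes in the flow diagram. State the rule, who applied it, what they could see, and whether it came before either partner was notified.
2. **Analyse as assigned.** Keep dyads in their final condition in the main and ITT analyses, subject to the inclusion rules already in the SAP.
3. **Adjust for baseline.** Add own and partner's baseline mean steps to the two step-change models, at least as a pre-specified sensitivity analysis, and to the two goal-attainment models as a further sensitivity analysis.
4. **Use the draws that agreed.** If the original draws exist, repeat the primary models in dyads whose two draws matched, as a sensitivity analysis.
5. **Otherwise, say so.** If neither a fixed blind rule nor the original draws can be shown, report this as a limitation and do not describe the allocation as fully randomised by dyad.

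Cost: a few sentences, two columns and some model reruns. Baseline adjustment keeps all analysed dyads but deals only with selection on recorded baseline steps. The analysis of agreeing draws uses about half the dyads, so its SE is about 1.4 times larger, and it needs draws that the documents do not say were kept.

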Analysis Plan

Study Title: Using Social Connectedness to Increase Physical Activity

Identifier: NCT04573972

Unique Protocol ID: STUDY2019_00000296

Date: October 22, 2021

Hypotheses

Hypotheses are pre-registered at ClinicalTrials.gov NCT04573972

<https://clinicaltrials.gov/ct2/show/NCT04573972>

We hypothesize that, compared to the regular incentive condition, participants in the social incentive condition will show a larger positive change in daily steps walked during the baseline period to daily steps walked in the post-intervention period.

Study Design

Participants volunteered for the study with a friend; thus randomization occurs at the level of the dyad, with half the dyads assigned to the regular incentive condition and half to the social incentive condition. During a 5-week protocol, participants complete a 1-week baseline period, a 2-week incentive period and a 2-week post-incentive period.

Communication with participants occurred using the Way to Health (W2H) platform. Participants downloaded the FitBit and Aware apps onto their IOS or Android smart phone to track steps walked and GPS location. They completed surveys on W2H at the beginning and end of the survey. W2H sent participants text messages each morning and evening. During the baseline period participants earned \$1 for each day they synced both apps. After the baseline period all participants were assigned a daily step goal that represented a 30% increase in daily steps walked. During the incentive and post-incentive periods, the evening text message included a link to a survey where participants could self-report walking with their partner. During both of these periods, participants earned \$1 per day for syncing the apps and an additional \$1 per day for completing the evening survey. During the incentive period only, they earn \$2 per day for meeting their step goal (regular incentive) or they earn \$1 per day for meeting their step goal and an additional \$1 per day for walking at least 1 mile with their partner. At the completion of the study, participants were mailed a ClinCard debit card loaded with their payment total.

Randomization

Simple randomization to condition was accomplished via the W2H platform at the completion of the baseline period. Because W2H does not have the capacity to randomize at the level of the dyad, the research team manually adjusted conditions such that both members of a dyad were in the same study condition.

Explanation of existing data

The study protocol was pre-registered at ClinicalTrials.gov NCT04573972 <https://clinicaltrials.gov/ct2/show/NCT04573972> prior to any data collection. Clinical Trials pre-registrations do not include analysis plans. Consequently, this OSF pre-registration, including an analysis plan, was filed prior to downloading any data from W2H.

Participant flow diagram: ([name] or [name], please fill in numbers)

XXX people entered W2H portal	→ XX did not consent
↓ XX consented	→ XX did not fully enroll
↓ XX fully enrolled	→ XX not linked to a fully-enrolled partner
↓ XX has fully-enrolled partner	→ XX did not provide synced FitBit & Aware data for at least 1 out of 7 days of pre-intervention period or has partner who did not provide synced data for 1 out of 7 pre-intervention days
↓ XX provides baseline data	→ XX requested to be unenrolled prior to randomization
↓ XX included in study and randomized to condition (N= XX/2 pairs)	
↓ XX in the regular incentive condition & YY in the social incentive condition	

Data collection procedures

Study participants were recruited at Carnegie Mellon University through posting on the subject pool website and announcements to undergraduate classes. Potential participants had to sign up with a friend, with at least one member of the friend pair being a current CMU student. Participants had to own an IOS or Android smartphone and be willing to download the FITBit and Aware apps to track their activity and location for 5 weeks.

Stopping rule

Our stopping rule was to close enrollment once 220 people were fully enrolled or when Oct 15, 2020 occurs, whichever comes first. We opened enrollment on Oct 1, 2020 and closed it on Oct 11, 2020 because at that point 220 people had fully enrolled. Fully enrolling includes consenting, completing the intake survey, providing a code for a partner who was also enrolling, and downloading the FitBit and Aware apps. Some of the individuals who fully enrolled were not included in the study because their partner did not fully enroll.

Manipulated variables

There was one manipulated variable (treatment condition) with two levels: regular vs. social incentive.

Measured variables

Primary dependent variables (as pre-registered on Clinical Trials)

1. The mean daily treatment period step count (averaged across all of a participant's included treatment period days) minus the mean daily baseline period step count (averaged across all of a participant's included baseline period days).
2. The mean daily followup period step count (averaged across all of a participant's included followup period days) minus the mean daily baseline period step count (averaged across all of a participant's included baseline period days).
3. Number of days during treatment period when participant reached goal. Converted to a fraction by dividing by the number of included treatment period days.
4. Number of days during followup period when participant reached goal. Converted to a fraction by dividing by the number of included followup period days.
5. Change in score on UCLA Loneliness Scale. Score on post-test (range 0 to 60) minus score on pretest.

Secondary dependent variables (as pre-registered on Clinical Trials)

6. Number of days participant walked together with partner during treatment period, as assessed via self-report on daily survey

7. Number of days participant walked together with partner during followup period, as assessed via self-report on daily survey
8. Number of days participant walked together with partner during treatment period, as assessed via Aware data
9. Number of days participant walked together with partner during followup period, as assessed via Aware data

Indices

The UCLA Loneliness Scale is measured on both the intake and exit surveys. It consists of 20 items, each scored as 0, 1, 2, or 3. The scores from all 20 items are added to form a total score ranging from 0 to 60.

Inclusion Criteria

In order to be included in the study, each participant must fulfill all of the following

- Consent
- Fully enroll, including authorizing FitBit app and installing Aware app
- Link to a friend who fully enrolls in the study before the registration deadline
- Participants who request to unenroll are excluded.
- Provide synced step data for at least one day of the 7-day baseline period
 - That is, there must be at least one baseline day with a non-zero step count
- Provide Aware data for at least one day of the 7-day baseline period

Exclusion of individual data points

- Days that a participant has a value of 0 for steps walked will be considered missing data (assume there was no sync for that day)
- For each participant, we will compute the mean and standard deviation of number of daily steps, computed over all days of the study with non-zero step counts. Days with a step count that are > 3 standard deviations away from the participant's own mean will be excluded from analyses (treated as missing data).
- Average step count will then be computed for each phase, after treating these excluded data points as missing.

Data File Structure

- Note: remove the research team participants from the datafile.
- Daily file (35 rows per participant -- one row per day of the protocol)
 - Subject id
 - Dyad id (links together the two subject ids in a friend pair)

- Phase (baseline, incentive, followup)
- Day of protocol (1 - 35)
- Calendar date
- FitBit steps walked
- Met goal (yes or no; missing for baseline period)
- Synced FitBit data (yes or no)
- Synced Aware data (yes or no)
- Correct end-of-day survey sent (yes or no; missing for baseline period)
- Answered end-of-day survey (yes or no; missing for baseline period)
- Walked with partner (yes or no; missing if wrong survey sent or survey not answered)
- Walked at least 2,000 steps with partner (yes, no, or missing)
- Walked in-person or virtually with partner
- Study file (1 row per participant)
 - Subject id
 - Included in study (for ITT analysis)
 - Included in main analysis
 - Dyad id (links together the two subject ids in a friend pair)
 - Date started baseline period
 - Date started incentive period
 - Goal number of steps
 - Total amount earned during study
 - All responses from baseline survey
 - All responses from exit survey

ITT analysis

- Includes all Ss who meet the inclusion criteria, even if they have a lot of missing data.
- Similar to the main analysis described below, but it doesn't exclude Ss based on missing data.
- It does still exclude individual data points, same as in the Main Analysis

Main Analysis

In order to be included in the main analyses, each participant must also fulfill all of the following

- Provide synced step data for at least 2 days of the 7-day baseline period
- Provide synced step data for at least 4 days of the 14-day treatment period
- Provide synced step data for at least 4 days of the 14-day followup period
- Be paired with a partner who is also included in the main analyses

Secondary Analyses

- Secondary analyses will explore the relationships among change in UCLA Loneliness score (intake to exit survey), change in mean daily steps walked from baseline to post-incentive period, and percentage of days during post-incentive period when the dyad walked together. Specifically, we will test whether the effect of study condition on change in steps walked is mediated by change in loneliness score and percentage of days when the dyad walked together.
- Two boot-strapped mediation analyses will be conducted, one for each putative mediator.

Primary dependent variables (as pre-registered on Clinical Trials)

1. The mean daily treatment period step count (averaged across all of a participant's included treatment period days) minus the mean daily baseline period step count (averaged across all of a participant's included baseline period days).
2. The mean daily followup period step count (averaged across all of a participant's included followup period days) minus the mean daily baseline period step count (averaged across all of a participant's included baseline period days).
3. Number of days during treatment period when participant reached goal. Converted to a fraction by dividing by the number of included treatment period days.
4. Number of days during followup period when participant reached goal. Converted to a fraction by dividing by the number of included followup period days.
5. Change in score on UCLA Loneliness Scale. Score on post-test (range 0 to 60) minus score on pretest.

Secondary dependent variables (as pre-registered on Clinical Trials)

6. Number of days participant walked together with partner during treatment period, as assessed via self-report on daily survey
7. Number of days participant walked together with partner during followup period, as assessed via self-report on daily survey
8. Number of days participant walked together with partner during treatment period, as assessed via Aware data
9. Number of days participant walked together with partner during followup period, as assessed via Aware data

Main Analysis

- DV = each of the primary dependent variables shown above
- IV = condition (regular vs. social incentive)
- Data structure: 1 rows of data per participant
- Errors clustered at the dyad level
- Covariates:
 - Partners in same or different time zone (dyad level)
 - Gender, age (individual level)
 - Date of first day of baseline (individual level)
 - Lag in number of days between enrollment of first partner and enrollment of second partner (dyad level)

Exploratory HLM Analysis

- DV = daily step count
- IV
 - Fixed effect of participant
 - Dummy variable for treatment period (relative to baseline period as reference)
 - Dummy variable for followup period (relative to baseline period as reference)
 - Interaction between each dummy & condition (regular vs. social incentive)
- Data structure: 35 rows of data per participant (one for each day)
- Clustering: days nested within participant; participant nested within dyad

Transformations

None planned.

Inference criteria

Alpha is set at .05

Data exclusion

See analysis plan

Missing data

When a participant is missing step data for an individual day, the mean daily step count for the study phase will be computed using the days with non-missing data. If a participant is missing step data for all the days in a study phase, the mean daily step count for the baseline period will be substituted (leading to a change score of 0).

If a participant is missing data from the intake survey (e.g., gender, age, or UCLA loneliness score), the study-wide mean or mode will be substituted. If a participant is missing data from the exit survey (e.g, UCLA loneliness score), the corresponding value from the intake survey will be substituted.
